14.4 Stratification Factors

Not applicable

14.5 Analysis plan

The main analysis of study findings will be done for all patients who meet evaluable criteria as stated in Section 14.3. As noted above, analyses of some secondary endpoints, including acute toxicity, psychosocial parameters, tissue and blood product-related biomarker distribution on US-guided biopsies, and initial MRI findings may be reported before the efficacy endpoints, including the primary endpoint. These secondary endpoints will be analyzed after all planned patients have been accrued, completed treatment and have a minimal potential follow-up of 3 months from the end of RT. An initial analysis of clinical outcome (efficacy) is planned after all patients have been assessed for PSA levels at 9 months and a final analysis will be done at the completion of the planned 5 year follow-up of all study patients. Statistical tests will be two-sided with 5% significance level.

Statistical analysis will include descriptive statistics for patient demographics and baseline disease characteristics. Counts and percentages will be used to summarize the distribution of categorical variables while median, range, mean and standard deviation will be used for continuous variables. Baseline characteristics will include age, race/ethnicity, PSA, PSA doubling time, pT-category, pathologic Gleason score, and performance status. Biomarker measurements and proteomic/genomic profiles obtained from baseline biopsy will also be summarized with descriptive statistics.[51]

Treatment received will be summarized by the number and duration of treatment delays, and the rates of discontinuation or completion. Safety analysis will include a detailed tabulation of acute and late occurring toxicity by type and grade. Additionally, we will estimate the cumulative incidence (from start of treatment) of grade 2+ and 3+ genitourinary (GU) toxicity and of grade 2+ and 3+ gastrointestinal

(GI) toxicity. Death without the toxicity of interest will be treated as a competing risk, and toxicity rates will be reported.

The primary trial endpoint, *PSA response rate*, will be estimated as a proportion with corresponding 95% confidence interval by the exact binomial method. Biomarker and proteomic/genomic characteristics of baseline prostate bed biopsy tissue will be summarized by descriptive statistics. Additionally, biomarker and proteomic/genomic characteristics measured in blood samples obtained at baseline, RT completion, and 3 months post RT will also be studied and changes from baseline will be tested for significance using t-test (means) or McNemar's test (proportions) for paired data. (For biomarker studies, nonparametric tests or data transformations to attain approximate normal distributions will be applied as needed.) Logistic regression models will be used to investigate the association between baseline factors, including biomarkers and proteomic/genomic profiles, and PSA response. Changes in biomarkers and proteomic/genomic characteristics measured in blood will also be investigated for association with PSA response.[52]

Patients will be followed for disease progression and vital status for a period of five years after completing study treatment. Progression of disease will be categorized as biochemical failure (BF), clinical failure (CF), or combined (BF + CF), where combined failure refers to documented evidence of BF and CF occurring within 6 months of each other with the earlier date used. CFs will be further categorized as local, nodal, or distant. Start of subsequent therapy will be considered a failure event for selected analyses as indicated in the table below. Deaths will be categorized as related/unrelated to prostate cancer. The number of observed failures will be tabulated by failure type. Similarly, vital status will be tabulated by presence or absence of disease at last follow-up.

Time to event endpoints will be analyzed by Kaplan-Meier (KM) or competing risk (CR) methods as indicated in Table 14.5.[53, 54] Where the Kaplan Meier method is used, point estimates and 2-sided 95% confidence intervals for event-free rates will be reported for selected times such as 1, 2 and 5 years from treatment start using Greenwood's variance and the log-log transform method. Median event-free or overall survival time, if attained, will also be reported. Cox regression models will be used to explore the prognostic effect of baseline characteristics as well as biomarkers and proteomic and genomic profiles. Regression findings will be expressed as hazard ratios and corresponding 95% confidence intervals. For analyses involving competing risks, cumulative incidence rates will be reported for selected times with corresponding 2-sided 95% confidence intervals based on the variance estimator of Aalen and the log-log transform method. Regression models investigating prognostic factors will be fit by the method of Fine and Gray. [55, 56] Where study data indicate that at most a small number of competing risk events have occurred, analysis will be simplified by treating such events as censored observations in a Kaplan-Meier analysis, since the resulting overestimation of the event rate will be negligible.

Table 14.5. Time-to-event endpoints.

Endpoint	Analysis	Events (earliest)	Competing risks	Censoring
Failure rate	CR	CF, BF, BF+ CF (within 6 months of each other). Start subsequent therapy. Death related to prca without prior evidence of failure.	Death unrelated to prca	Last clinical +PSA assessment
Toxicity rate (to be done separately for GI and GU)	CR	Onset of grade 2+ and 3+ toxicity	Start subsequent therapy Death, any cause	Last contact
Failure free survival (FFS)	KM	CF, BF, BF+ CF. Start subsequent therapy. Death, any cause.	n/a	Last clinical or PSA assessment
Prostate cancer mortality	CR	Death related to prca	Death unrelated to prca	Last contact
Overall survival (OS)	KM	Death, any cause	n/a	Last contact

KM: Kaplan-Meier. **CR:** competing risk. **BF:** Biochemical failure. **CF:** clinical failure. **prca:** prostate cancer. **GI:** gastrointestinal. **GU:** genitourinary.

QOL scores will be calculated in accordance with established scoring methods for each instrument. Descriptive summaries of scores at baseline and each subsequent follow-up will include median and range, means and standard deviations. Where criteria for clinically meaningful differences have been established, we will also categorize changes in these scores (computed by subtracting baseline from subsequent score) as indicating improvement, worsening, or no change and summarize these by counts and percentages. Further analysis allowing for repeated measurement will be conducted using mixed models.

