14.2 Sample size, accrual rate and study duration

Sample size is based on the primary objective of demonstrating that MTSRT increases the rate of PSA response to treatment, by which we mean undetectable PSA level (<0.1) when assessed 21 months after completing treatment. We expect the PSA response rate in the standard SRT to be 60%. [50] Assuming sufficient follow-up to determine PSA nine months post treatment, a total of 40 patients in the single-arm study provides 83.9% power to detect an absolute increase of 20% in the PSA response rate, from 60% to 80%, using a one-sided Fisher's exact test with 5% significance level. To ensure a minimum of 40 study patients evaluable for PSA response as our main study endpoint, we plan to enroll a total of 44 patients assuming 10% drop-out.

We plan to accrue 1 patient per month during the first year of this protocol. After the ramp-up phase is completed, we anticipate 1.5 patients per month. This rate was also calculated considering increasing prostate cancer volumes due to expansion of the department (anticipated growth at Sylvester main and Deerfield branch). Thus accrual will be complete in about 3 years; 12 in year 1 and 18 per year in year 2 and 3. Patients will be followed for a minimum of five years, giving total study duration of 8 years. The main efficacy endpoint will be analyzed after enrollment is complete and all patients have been

assessed for PSA response nine months post treatment, and a final efficacy analysis of all endpoints will be carried out at the conclusion of study when patients have been followed for 5 years. Analyses of some secondary endpoints, including acute toxicity, psychosocial parameters, and biomarker distribution on US guided biopsies, and initial MRI findings may be reported before the efficacy analyses. These secondary endpoints will be analyzed after all planned patients have been accrued, completed treatment and have a minimal potential follow-up of 3 months from the end of RT.

14.3 Definitions and endpoints:

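### Section 14.5 relates markers to PSA response by logistic regression at a flat 5% level, with no provision for sparse data or for many tests

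*Combined protocol and SAP*

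**What the plan says.** Section 14.5 (Analysis plan) commits to this: "Logistic regression models will be used to investigate the association between baseline factors, including biomarkers and proteomic/genomic profiles, and PSA response". It adds that changes in the blood markers will be examined against PSA response in the same way. The general rule in that section is "Statistical tests will be two-sided with 5% significance level", with no exemption for marker work. For the time-to-event endpoints, "Cox regression models will be used to explore the prognostic effect of baseline characteristics as well as biomarkers and proteomic and genomic profiles".

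The section names seven baseline characteristics in its descriptive paragraph and does not count the biomarkers or profile features. It gives no limit on predictors, no selection rule, no method for sparse outcomes and no multiplicity adjustment. Its allowance for nonparametric tests and transformations follows the paired-change tests and deals with distributional shape.

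Section 2.2 makes the relationship of circulating DNA and tumor cells to biochemical response a secondary objective, and sections 4.8 and 8.0 say it will be tested. Section 4.7 calls the blood proteomic and genomic analyses exploratory.

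The outcome counts follow from section 14.2, which sets a reference rate of 60% and a target of 80%, tested one-sided. It states that "a total of 40 patients in the single-arm study provides 83.9% power to detect an absolute increase of 20% in the PSA response rate".

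**The concern.** A logistic model draws its information from the smaller outcome group. If the trial meets its own target, that group has about 8 men. When every marker-positive man responds, or none does, the maximum-likelihood odds ratio is infinite or zero and its Wald interval is meaningless. Separately, a flat 5% rule over an uncounted list of markers will produce apparent associations when none exist.

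At stake is how far the marker results can be relied on, including those for the listed CTC and fcDNA objective. The primary response rate does not depend on these models, because section 14.5 estimates it as a proportion with an exact binomial interval.

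**Working it through.** **Inputs.** N = 40 evaluable; response 60% (reference) and 80% (target), section 14.2. Prevalence of the adverse fcDNA/CTC group 10-15%, Hypothesis 3. Detectable CTCs in over 30% of patients, section 8.0. Two-sided 5%, section 14.5.

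**1. The plan's own figure.** A one-sample exact binomial test that rejects at 30 or more responders of 40 has P(X ≥ 30 | 0.60) = 3.5% and P(X ≥ 30 | 0.80) = 83.9%. This reproduces the stated power and confirms the design rates.

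**2. Non-responders.** 40 × (1 − 0.80) = 8 (95% binomial range 3 to 13). 40 × (1 − 0.60) = 16 (range 10 to 22).

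**3. One binary marker, no true association.** Let π be the prevalence and r the response rate. The odds ratio is not finite when a cell of the 2×2 table is empty:

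- A: no marker-positive non-responder, [1 − π(1 − r)]^40
- B: no marker-positive responder, (1 − πr)^40
- C: no marker-positive man at all, (1 − π)^40, counted in both A and B, so subtracted once
- D: what the marker-negative cells add, about [1 − (1 − π)(1 − r)]^40 − r^40 at 80% response, and under 0.0001 at 60%

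| π | r | A | B | C | D | A + B − C + D |
|---|---|---|---|---|---|---|
| 10% | 80% | 0.4457 | 0.0356 | 0.0148 | 0.0002 | 47% |
| 12.5% | 80% | 0.3632 | 0.0148 | 0.0048 | 0.0003 | 37% |
| 15% | 80% | 0.2957 | 0.0060 | 0.0015 | 0.0004 | 30% |
| 30% | 80% | 0.0842 | 0.0000 | 0.0000 | 0.0022 | 9% |
| 10% | 60% | 0.1954 | 0.0842 | 0.0148 | 0.0000 | 26% |
| 12.5% | 60% | 0.1285 | 0.0442 | 0.0048 | 0.0000 | 17% |
| 15% | 60% | 0.0842 | 0.0230 | 0.0015 | 0.0000 | 11% |
| 30% | 60% | 0.0060 | 0.0004 | 0.0000 | 0.0000 | 0.6% |

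A and B depend only on the response rate among marker-positive men. The 60% rows therefore also describe, closely, an adverse marker whose carriers respond at 60% while the other men do better.

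**4. One continuous marker.** In 1,000 simulated null trials per setting, separation occurred in 0.1% at 80% response and 0% at 60%.

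**5. A profile.** An intercept plus 39 linearly independent features gives 40 columns for 40 men. Such a model fits any pattern of responses perfectly, so separation is certain.

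**6. Many tests.** For K independent null tests at 5%, P(at least one false positive) = 1 − 0.95^K:

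- K = 7: 30%
- K = 20: 64%
- K = 100: 99%, with 100 × 0.05 = 5 expected false positives

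Simulated screens of single continuous markers at 80% response (500 runs) fall on either side of this formula. Wald tests gave 24% for 7 markers and 51% for 20; likelihood-ratio tests gave 36% and 72%.

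**7. The remedy.** Firth logistic regression with penalised likelihood-ratio tests was simulated for one null binary marker (n = 40, prevalence 10-30%, response 80% and 60%, 2,500 runs per setting). Every log odds ratio was finite, with the largest below 4 in absolute value. The false-positive rate was 2.4-4.4%.

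**The case against.** The strongest reply is that this is exploratory work with no decision attached. Section 4.7 uses that word for the blood proteomic and genomic analyses, and the verbs in section 14.5 are to investigate and to explore. That holds and keeps the severity low. It does not close the gap: the CTC and fcDNA relationship is a listed objective, the 5% rule exempts nothing, and an exploratory estimate still has to exist.

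Second, the markers are largely quantitative (CTC counts, fcDNA concentrations), and section 8.0 expects detectable CTCs in over 30% of men. This also holds. A reader might infer that odds ratios will often fail to exist across the whole marker programme. The figures do not support that: the failure belongs to uncommon binary markers and high-dimensional profiles.

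Three other stronger readings should be set aside.

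- A reader might infer that the tests are generally anti-conservative. At 80% response with one continuous predictor, simulated size was 2.8% for Wald and 5.1% for likelihood ratio. Wald size stayed at about 3-4% with 2 to 10 predictors. Clear inflation appeared only for likelihood-ratio tests in models with several predictors.
- A reader might infer that all seven baseline characteristics enter one model with a marker. Section 14.5 lists them for description and specifies no such joint model.
- A reader might infer that these models are what the next trial will be designed on. Section 14.1 gives that role to the evaluation of PSA response itself.

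Maximum likelihood is inferred from the plan's silence; no estimation method is named.

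**Conclusion.** The concern holds in a limited form. If the 80% target is met, an uncommon binary marker of the kind in Hypothesis 3 has no finite odds ratio in roughly one trial in three to one in two. At the 60% reference rate this is about one in nine to one in four. For markers near 30% prevalence it is under one in ten, and for single continuous markers it hardly ever happens. Without multiplicity control, a panel of 20 or more null markers is more likely than not to yield at least one nominally significant result.

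These sizes assume no true association, independent markers (correlation would lower the family-wise figures), all 40 men contributing data, and Hypothesis 3's percentage read as marker prevalence. Tissue markers come only from men who accept the optional biopsy, so fewer men may contribute to them.

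This is a cheap improvement of low severity.

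**What to change.** In section 14.5:

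- Fit the associations of markers and profiles with PSA response by Firth penalised logistic regression, with profile-likelihood intervals.
- Replace the flat 5% rule for these analyses by Benjamini-Hochberg control of the false discovery rate within each marker panel, with the panels and the rate stated in advance.
- Report the results as hypothesis-generating.

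The Firth check above covered one binary marker at a time, so it is no evidence about a joint fit of a whole profile; the section should say how profile features enter the model. The documents give no basis for barring multivariable models. No event count was worked out that would justify asking for penalised Cox models.

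The cost is a few sentences and standard software, with no change to patients, visits or samples. The downside is that fewer markers will be called significant.

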1.0 BACKGROUND

1.1 Study Disease

Despite considerable advances in radiation delivery methods and assessing patient risk by integrating PSA parameters into decision-making for men with a rising PSA post-prostatectomy, failure rates from Salvage Radiotherapy (SRT) are relatively high overall[1, 2] and there is poor understanding of which patients are curable with standard SRT doses. Since on average about half of these men will experience a biochemical failure within 5 years after SRT, and over 30% of men undergoing radical prostatectomy will be referred for salvage radiotherapy, this is a management problem of enormous magnitude. The analysis of biomarkers is expected to improve upon the risk assessments now in practice and provide much needed molecular information that could lead to targeted therapeutic breakthroughs later.

The measurement of biomarkers from tissue in men being considered for SRT is confounded by reliance on the tissue from the prostatectomy specimen. Some studies indicate that the prostatectomy tumor tissue is representative when biomarkers are performed.[3] We plan to request archival prostatectomy tissue (if available in the Department of Pathology) for biomarker assessment and also to obtain biopsies of the surgical bed under US guidance. The biopsy of functional MRI-defined regions for biomarker analysis has never before been described to our knowledge.

Recent MRI imaging data from our group[4] and others[5-7] indicate that part of the problem with the efficacy of SRT may stem from the fact that about 70% have identifiable functional imaging abnormalities in the prostate bed, suggesting bulkier disease than previously appreciated using CT or by digital rectal exam. Radiation doses used for SRT have traditionally been low based on the belief that the disease is subclinical and microscopic. The realization of larger lesions in a potentially hypoxic environment might best be treated with a more aggressive SRT dosing strategy.

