9.1 Definitions

- *PSA response rate*: The proportion of study patients with PSA <0.1 ng/mL at 21 months after completion of study treatment.
- *Acute toxicity*: Toxicity occurring during treatment and within three months of completing treatment.
- *Late toxicity*: Toxicity occurring more than three months after treatment completion. *Failure rate*: The cumulative incidence of biochemical or clinical failure allowing for competing risk as needed. Clinical failure is defined as at least a 25% increase in the size of the tumor relative to the smallest volume recorded, or new extension of tumor beyond the capsule, or re-extension of tumor beyond the capsule after initial regression, or urinary obstructive symptoms with carcinoma found at TURP. Biochemical failure is defined as PSA \geq nadir + 2 ng/mL.

- *Failure-free Survival (FFS)*: The elapsed time from start of radiotherapy to first documented evidence of biochemical or clinical failure or death from any cause, whichever occurs first. In the absence of any event defining failure, follow-up time will be censored at the date of last documented failure-free status.
- *Overall Survival (OS)*: The elapsed time from start of radiotherapy to death from any cause. For surviving patients, follow-up will be censored at the date of last contact.
- *Biomarker expression*: Quantification of the amount of the biomarker specific immunohistochemical staining in the area of tumor.
- *QOL*: Two contemporary instruments will be utilized to assess patient function and bother (Expanded Prostate Cancer Index Composite-SF12 (EPIC-SF12) and prostate cancer-specific anxiety Memorial Anxiety Scale for Prostate Cancer patients (MAX-PC).

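### Section 14.5 lets an undefined small count of competing events switch three secondary endpoints from cumulative incidence to Kaplan-Meier: a minor, upward-only error that is free to remove

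*Combined protocol and SAP*

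**What the plan says.** Section 14.5 fixes the method for each endpoint in advance: "Time to event endpoints will be analyzed by Kaplan-Meier (KM) or competing risk (CR) methods as indicated in Table 14.5". The table marks failure rate, toxicity rate (GI and GU separately) and prostate cancer mortality as CR. Failure-free survival and overall survival are marked KM.

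For the CR rows the estimator is specified: "For analyses involving competing risks, cumulative incidence rates will be reported for selected times", with the Aalen variance and log-log intervals. On regression the text says "Regression models investigating prognostic factors will be fit by the method of Fine and Gray".

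The same paragraph then adds an exception. Its trigger is "Where study data indicate that at most a small number of competing risk events have occurred". Its consequence is that "analysis will be simplified by treating such events as censored observations in a Kaplan-Meier analysis". The reason given is "since the resulting overestimation of the event rate will be negligible". The plan gives no number for the trigger and no bound for what counts as negligible.

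Section 9.1 defines the failure rate with a similar qualifier: "The cumulative incidence of biochemical or clinical failure allowing for competing risk as needed".

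**The concern.** The exception makes the estimator for three of the five time-to-event endpoints depend on a count seen in the data and judged against an unstated limit. Two analysts with the same data could report different failure rates and both be following the plan.

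The error has one direction. Censoring a man who dies of another cause treats him as if he could still fail later at the same rate as the men still at risk. That spreads his weight over later failures and pushes the estimated failure probability up.

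Each analysis has its own competing-event count, so failure, GI toxicity, GU toxicity and cancer mortality could end up on different estimators in one report. Toxicity is the most exposed. Table 14.5 lists starting subsequent therapy, as well as death, as a competing event there, and Section 1.1 expects frequent failure: "Since on average about half of these men will experience a biochemical failure within 5 years after SRT". Starts of subsequent therapy may therefore not be rare, and whether a given number still counts as small is left to judgement.

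**Working it through.** **The plan's own figure.** The exception states no number, so there is none to reproduce. The only power figure (83.9%, Section 14.2) belongs to the primary endpoint and does not depend on this clause.

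**Inputs from the documents.** 40 evaluable men (Section 14.2); about half failing biochemically within 5 years (Section 1.1); five years of follow-up (Section 14.5).

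**Assumed inputs.** The number and timing of competing events, and exponential failure times. The documents give none of these, so a range is shown.

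**Step 1: closed form.** Let F be the 5-year cumulative incidence of failure and C that of competing events, with constant hazards a and b.

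- 5(a+b) = −ln(1−F−C)
- 5a = [F/(F+C)] × 5(a+b)
- 1-KM = 1 − exp(−5a)

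For F = 50% and C = 10% (4 of 40): 5(a+b) = −ln(0.40) = 0.9163; 5a = 0.9163 × 0.50/0.60 = 0.7636; 1-KM = 53.4%.

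| F | C = 5% (2 of 40) | C = 10% (4 of 40) | C = 15% (6 of 40) |
|---|---|---|---|
| 50% | 51.6% | 53.4% | 55.4% |
| 45% | 46.4% | 48.0% | 49.7% |
| 30% | 30.9% | 31.8% | 32.9% |

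**Step 2: simulation at N = 40.** There were 3,000 data sets per setting, with competing events at random times. Each entry is the mean excess of 1-KM over the cumulative incidence at 5 years, in percentage points. The left column is the event level as 1-KM estimates it.

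| Event level | 1 event | 2 | 4 | 6 | 10 |
|---|---|---|---|---|---|
| 50% | 0.8 | 1.6 | 3.1 | 4.7 | 7.8 |
| 20% | 0.3 | 0.5 | 1.1 | 1.6 | 2.7 |
| 10% | 0.1 | 0.3 | 0.5 | – | 1.3 |

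The 50% row is slightly below Step 1 because the simulation holds 1-KM at 50% and lets the cumulative incidence fall, while Step 1 does the reverse. The two agree when matched. With 4 events the simulated cumulative incidence is 46.8%; putting F = 0.4679 and C = 0.10 into Step 1 gives 1 − 0.4321^(0.4679/0.5679) = 49.9%, which is the simulated 1-KM.

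**Step 3: direction.** In no simulated data set was 1-KM below the cumulative incidence. With no competing events the two were identical. They were also identical (50.0% each) in a constructed data set where both competing events came after the last of 20 failures. With one competing event they were equal in about 5% of runs at the 50% level and 13% at the 20% level.

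**Step 4: extreme timing.** If all c competing deaths come before any of 20 failures, the cumulative incidence is 20/40 = 50% and 1-KM is 20/(40−c): 51.3% for c = 1, 52.6% for 2, 55.6% for 4 and 66.7% for 10.

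**Step 5: scale.** The 95% half-width for a proportion of 50% in 40 men is 1.96 × √(0.5 × 0.5/40) = 15.5 points.

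**The case against.** The strongest defence is that the plan is open about what it does. The exception is written in advance, names the overestimation and confines itself to few competing events. Read as one or two events, its claim of a negligible effect is fair: 0.3 to 1.6 points on average at the 20% and 50% levels, against a half-width near 15. A switch at 6 or 10 events would sit badly with the plan's own condition. The counts used above are assumptions, and the upper age limit of 85 is an eligibility bound, not an expected age. For failure rate the competing event is only death unrelated to prostate cancer before any failure, which is narrower than all deaths. All of this stands, and it is why the point is minor.

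Four stronger readings are tempting but unsupported.

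- **That the switch always overstates.** It never understates, but the two estimates can coincide (Step 3).
- **That it lets the sponsor pick a favourable result.** The trigger is the competing-event count, not the failure result. The error makes failure, toxicity and cancer death look worse, so it cannot flatter the boost.
- **That regressions would move from Fine and Gray to Cox.** The sentence speaks only of a Kaplan-Meier analysis and the event rate. It does not mention regression.
- **That the main conclusion is at risk.** The primary endpoint is a proportion with an exact binomial interval, and toxicity stopping in Section 14.6 uses patient counts, not these curves.

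What the defence does not supply is a reason to keep the exception. The stated aim is simplification, yet the cumulative-incidence estimator is already specified, is valid for any number of competing events, and equals 1-KM when there are none.

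**Conclusion.** The point holds as a minor one. For the three CR rows of Table 14.5, the plan replaces a valid, prespecified estimator with one it acknowledges is biased upward, on a trigger it does not define. At about 50% failure in 40 men, the mean excess is roughly 0.8 to 1.6 points for 1 to 2 competing events, 3 for 4 and 5 for 6. At a 20% event level it is about 1 point for 4 events. These sizes rest on assumed counts, exponential failure times and random timing of competing events; early clustering raises them (5.6 points for 4 events in the extreme case).

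The open cutoff could matter most for toxicity because more kinds of event compete there. Even so, at toxicity rates of 10% to 20% the mean excess with 10 competing events is 1.3 to 2.7 points. Only secondary, descriptive estimates are affected. The primary endpoint, power, significance level and stopping guidelines are not.

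**What to change.** Delete the sentence in Section 14.5 that permits the switch. State instead that every row marked CR in Table 14.5 is reported as cumulative incidence with the Aalen variance, and with Fine and Gray for its regressions, whatever the number of competing events. In Section 9.1, remove *as needed* from the failure-rate definition or point it to Table 14.5.

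The cost is one sentence and two words. No new method, data or programming is required, because the competing-risk analysis is already planned.

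If the sponsor prefers to keep the option, the second-best course is to state a numeric cutoff for each endpoint, report the cumulative incidence alongside the Kaplan-Meier figure, and say which regression model applies.
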